University of Miami - Miller School of Medicine

Set-Enhanced Aftercare for Mothers in Substance Abuse Recovery and Their Children

Version Date 6-7-2016

National Clinical Trial Number: NCT02702193

[name]

4. Description of Study

Study Protocol

4.1. * Abstract and Specific Aims

Include a brief summary of the significance, purpose or research question, specific aims, and risks/benefits. Specific aims include hypotheses you will investigate.

The study will conduct a translational randomized trial comparing an adaptation of Structural Ecosystems Therapy (SET), "Healthy Home", as an enhancement of substance abuse or mental health outpatient treatment, to outpatient treatment as usual (TAU) among approximately 172 Black, Hispanic and White non-Hispanic mothers enrolled in outpatient substance abuse, mental health or substance abuse as a co-occurring condition treatment. The study will be conducted with a community partner, Banyan Health Systems (also known as Miami Behavioral Health and Spectrum Programs), that delivers integrated substance abuse/mental health treatment and primary care. Agency staff will conduct data collection and agency nurses will deliver Healthy Home. Data will be collected at baseline and 4, 8, and 12 months post-randomization.

The Specific Aims of the proposed study are to:

- 1) test the effectiveness of SET for improving physical and mental health and reducing relapse of mothers in substance abuse/mental health recovery;
- 2) test the effectiveness of SET for improving health and mental health outcomes of children of mothers in recovery;
- 3) test mechanisms of action of SET (self care, environmental risk, family functioning and stigma);
- 4) assess SET implementation and sustainability factors and the relationship between fidelity and outcomes; and
- 5) examine the interactions of ethnicity and ethnicity-related factors on outcomes.

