Child medical condition Measure. This measure combines items from the Caregiver Strain Questionnaire (Brannan, Heflinger, & Brickman, 1997) and modified items from the Early Childhood Longitudinal Survey-Birth Cohort questionnaires. The measure with Spanish and English items is attached in Supporting documents. For this study, 1 item will assess whether a child has any medical condition, and what condition, if one exists. 9 items will assess the strain associated with the condition on a 5-point Likert scale. 2 items will assess whether the child receives services for the condition (e.g., speech therapy), and where services are received (e.g., school, home). 1 item asks for the number of hours received on average per week. The Caregiver Strain measure was used, in Spanish and English, in a previous IRB-Approved study (20070334) and the other items were translated from English into Spanish using a translation-back translation process for this study (statements attached in supporting documents).

The measure will be administered at baseline. If enrolled mothers have already completed the baseline, they will complete the form at one of the follow-up assessments. If participants have already completed all of the assessments, then study staff will attempt to contact the participant to complete the measure by phone.

We are requesting a Waiver of Signed Consent for this measure for the only participants who have already completed their baseline and all other assessments. They will answer these questions by phone to complete this measure. The Waiver is requested to avoid burdening participants who have already signed consent forms for this study, and would have to schedule an additional meeting to complete the consent form for this measure.

Mediator variables.

- Mother Self-care: Health Care Use will be assessed using the Stanford Health Care Utilization (Lorig, Stewart, Ritter, Gonzalez, Laurent, & Lynch, 1996) plus items from El Centro Demographics Scale and using two questions about recency of physical check-up and Pap test. Dental Care Use will be assessed using the Florida Dental Health Survey (Gilbert & Litaker, 2007). Form 90 Treatment/Living Experiences subscale (Tonigan, Miller, & Brown, 1997) and substance abuse treatment attendance records from Banyan will assess use of substance abuse services and self-help groups.

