- Family Functioning will be measured with the family cohesion subscale of the Family Environment Scale (Moos & Moos, 1981). Family Coping will be measured with two subscales from the Family-Crisis Oriented Evaluation Scales (F-COPES; McCubbin, Larsen, & Olsen, 1996).
- Social Support will be assessed using the Important People Interview (Clifford & Langabuagh, 1991).
- Stigma will be measured using a version of a Stigma scale (Ahern, Stuber, & Galea, 2007).
- Maternal Parenting Functioning will be assessed using the Parenting Practices Questionnaire (Gorman-Smith, Tolan, Zelli, & Huesmann, 1996) and Parenting Self Agency (Dumka, Stoerzinger, Jackson & Roosa; 1996) .

Moderator Measures

- Ethnicity (Black, Hispanic, White non-Hispanic), Socio-economic Status and general demographic information will be collected using demographics items from El Centro and other UM IRB-approved studies.
- Household Composition and Stability will be collected using a Household Composition Form.
- Mother's Stress will be assessed using the Hassles Scale (DeLongis, Folkman, & Lazarus, 1988)
- Mother's Abuse and History of Abuse will be measured using the Violence Scale (Peragallo, 2005).
- Mother's Sleep will be assessed with 4 items regarding sleep from the PROMIS-29 Health Scale.

We will be extracting some information from our intervention clinical forms to capture some of our research constructs. This information includes data related to health assessments, recommendations/referrals, treatment/services rendered, follow-up plan of care, and education. The data collection form has been created in RedCap (Research electronic data capture), an electronic data capture software. A table demonstrating items extracted from the clinical forms is uploaded to the eprost protocol. These clinical forms are kept in the locked research vault at the School of Nursing and Health Studies and will be protected at all times. RedCap data will be kept in password protected files.

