4.4.A. Standard Measures: Click the "Add" button to open the search window, then click the "Find" button to browse and select measures.

Name of Measure	Brief Description	Type of Measure
There are no items to display		

NOTE: A copy of the first page of each standard measure is provided in the [Library of Standard Measures](#) for verification. Ensure that the version being used in this study is the same as the version that has been selected.

Upload any questionnaires and/or assessment tools to be used that are not listed above:

Name	Description Version
Child Behavior Checklist Preschool CBCP.040813.docx	0.01
Child Behavior Checklist Schoolage CBCS.040813.docx	0.01
CHILD DEMOGRAPHIC INTAKE FORM CDIM.docx	0.03
Child Health Questionnaire Physical and Fam Scales Child Report CHQC.041013.docx	0.01
Child Health Questionnaire Physical CG and Family Scales Mother Report CHQM. 041013.docx	0.01
Child's BMI BMIC.040913.docx	0.01
Family Environment Scale Cohesion FES.040913.docx	0.01
FCO FCOPES bilingual.docx	0.01
FI Dental Care Study Child Rating FDSC.040813.docx	0.01
FL Dental Care Study Mother Rating Child FDSM.040813.docx	0.01
FL Dental Care Study Mother rating herself FDSW.040813.docx	0.01
Healthy Home Hassles Scale (HHH).docx	0.01
Healthy Home Important People Interview (IPI) English.docx	0.01
Healthy Home Important People Interview (IPI) Spanish.docx	0.01
HLF Health Literacy Screener HLF.041513.docx	0.01
Household Composition Form HCF.040913.docx	0.01

MDIF Mother Demographic-Translation v2.doc	0.05
Measures_Table_for IRB protocol.04-16-2013.docx	0.01
Modified Stigma Scale with Alcohol MSS.040913.docx	0.02
MSF (Mother Screening Form) with mental health.010914.	0.01
Oral Health Impact Scale Mother rating self OHIP.040913.docx	0.01
Pap Smear Last Check Form LCF.040913.docx	0.01
Parenting Practices Child Report PPC.041013.docx	0.01
Parenting Practices Parent Report PPP.040813.docx	0.01
Parenting Self Agency PSA.040813.docx	0.01
PER--Parent Relationship With Peer Group-Parent (English).doc	0.01
PER--Parent Relationship With Peer Group-Parent (Espanol) (DD).doc	0.01
PROMIS SF v1.0 - ED-Anxiety-SF8a Spanish.pdf	0.01
PROMIS SF v1.0 - ED-Anxiety-SF8a.pdf	0.01
PROMIS SF v1.0 - ED-Depression-SF8a Spanish.pdf	0.01
PROMIS SF v1.0 - ED-Depression-SF8a.pdf	0.01
SET-R Addiction Severity Index LITE (ASI).RX accomodation.docx	0.01
SET-R Form 90 (F90).doc	0.01
SET-R PROMIS 29 Profile ENGLISH.docx	0.01
SET-R PROMIS 29 Profile SPANISH.docx	0.01

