-Testing hypothesized differences between experimental and control groups will use an intent-to-treat analysis that includes all participants randomized. LGM will examine the effect of treatment condition on trajectories of change separately for each of the outcomes over the one-year follow-up. To test Hypothesis 1, we will assess the trajectories of the mothers' outcomes (mental health, physical health, substance abuse, etc.) and predict of the trajectory of change by intervention condition (Healthy Home vs. TAU). Controlling for the effects of socio-demographic variables and pretest levels of the dependent variables is possible in LGM, if these variables are found to differ by randomization group. To test Hypothesis 2, a similar procedure will consider children's outcomes (mental health, physical health, behavior problems, etc.).

- Testing mechanisms of action. Using Mplus 6, this set of analyses will investigate links between trajectories of change (growth curves) for the hypothesized mechanism of action variables (mediators) and trajectories of mothers' outcomes or children's outcomes following MacKinnon, Lockwood, Hoffman, West and Sheets' (2002) procedures. This method is more powerful than the classic (Baron & Kenny, 1986) method, particularly for binary outcomes. LGM can also test multiple indirect paths or mediators (i.e., Hypothesis 3c) with this method.

- Clinically significant change procedures (Jacobson & Traux, 1991) can also investigate efficacy of an intervention. These procedures: 1) determining whether participants have made statistically reliable change and 2) categorizing subjects according to clinically meaningful cut-points, e.g., recovered (statistically reliable change that moves a client out of clinical range), improved (statistically reliable improvement, but still in the clinical range), and unimproved/deteriorated.

-Implementation analysis will be used to determine the feasibility of adapting Healthy Home for other agencies. Using cost logs for training and service delivery, the total cost of

implementing Healthy Home can be determined. Therapist and agency satisfaction as well as therapist fidelity to Healthy Home will be assessed to determine if changes to the Healthy Home implementation protocol are needed.

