To be eligible for the study Mothers must meet all of the following criteria: (1) Enrolled in outpatient substance abuse or mental health treatment (or treatment for substance abuse as a co-occurring disorder) or case management for mental health or substance abuse problems, (2) have at least one child age 0-17 with whom she has at least monthly contact (3) be age 18 or above, (4) capable of giving informed consent and comprehending either English or Spanish, (5) willing and able to participate fully in the protocol (e.g., to accept assignment to either condition, to provide sufficient locator information for follow-up, to allow their treatment sessions to be monitored for fidelity/process assessment and supervision).

To be eligible for the study Children must meet all of the following criteria: (1) biological, step or adopted child of a mother enrolled in the study and with whom the mother has at least monthly contact (2) age 2-17, (3) has the signed permission of a legal guardian to enroll in the study, (4) gives assent to participate in the study if age 7 or above.

5.8. * Will only one group of individuals be systematically selected and recruited for this study (e.g., welfare patients, racial and/or ethnic minorities, persons confined to institutions or persons determined to be incapacitated)?

Yes No

5.8.A. If yes, please state how this participant group will benefit from the results of the research and provide the reasons and justifications to target this group:

This study focuses on women in substance abuse/mental health treatment and their children. These groups are at high risk for significant health consequences and there is a need for culturally-informed interventions tailored to address their unique needs.

5c. Research Involving Pregnant Women or Fetuses

Pregnant woman or fetuses may be involved in research if **ALL** of the following conditions are met (all items must be justified):

(a) **Where scientifically appropriate, preclinical studies, including studies on pregnant animals, and clinical studies, including studies on nonpregnant women, have been conducted and provide data for assessing potential risks to pregnant women and fetuses.**

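### The treatment-use indicator of the self-care mediator covers only substance abuse services, yet mothers in mental-health care alone are eligible and are pooled into the same mediation models

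*Combined protocol and SAP*

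**What the plan says.** Aim 3 in section 4.1 is to "test mechanisms of action of SET (self care, environmental risk, family functioning and stigma"). Treatment use is not a mechanism of its own; it is one indicator of self care.

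Under Mediator variables in section 4.4, that indicator comes from a Form 90 subscale and "substance abuse treatment attendance records from Banyan", which together "will assess use of substance abuse services and self-help groups". The other self-care indicators are general health-care use, recency of check-up and Pap test, and dental care use. No measure of mental-health attendance is named.

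Criterion 1 for mothers in section 5.7 reads "Enrolled in outpatient substance abuse or mental health treatment (or treatment for substance abuse as a co-occurring disorder) or case management", and the case management may be for either kind of problem. The recruitment text in section 4.4 also accepts women treated at centers other than Banyan.

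The mechanisms paragraph of section 4.12 examines "links between trajectories of change (growth curves) for the hypothesized mechanism of action variables (mediators") and the outcome trajectories. It does not restrict or re-score by treatment track. Elsewhere 4.12 allows baseline covariates only when they are found to differ between the arms. Track is not among the moderators in 4.4. The data-quality paragraph of 4.12 offers transformations and count distributions, but no rule for scores that do not apply.

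**The concern.** A mother in mental-health care alone can attend every visit of her own treatment and still record no substance abuse service. The same zero in a mother in substance abuse treatment means that she did not attend. The mediation model cannot tell the two apart.

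Two things follow. First, mothers who cannot move on the mediator pull the arm-to-mediator path towards zero. Second, the mediator partly becomes a marker of treatment track. Any difference between tracks on the outcome, which is plausible for substance use and for mental health, then leaks into the mediator-to-outcome path. Randomisation does not protect that path. Because randomisation should balance track across arms, the covariate rule in 4.12 would seldom bring track into the model. At stake is the reading of Aim 3 for this indicator.

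**Working it through.** **Inputs.** From the documents: about 172 mothers (4.1), the eligibility rule (5.7), the indicator (4.4) and the pooled analysis (4.12). The plan gives no share of mothers in mental-health care alone, no mediated effect and no power calculation, so there is no planned figure to reproduce. Everything below is assumed:

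- a share p of mothers is in mental-health care alone and scores zero on the mediator in both arms, with p = 0.10, 0.30 or 0.50;
- in the other mothers, the arm effect on the mediator is a = 0.5 SD and the mediator-to-outcome slope is b = -0.3, so the indirect effect is 0.5 × (-0.3) = -0.150;
- allocation is 1:1, and the mediator and outcome residuals have SD 1.

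**Step 1: arm-to-mediator path.** In all mothers, a_all = (1 - p) × a = 0.45, 0.35, 0.25. The loss equals the share: 10%, 30%, 50%. If the tracks do not differ on the outcome, b stays at -0.3 and the indirect effect is -0.135, -0.105, -0.075.

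**Step 2: mediator-to-outcome path.** Let d be the outcome difference (substance abuse or co-occurring minus mental-health-only) at a given mediator value, in residual SDs, with higher meaning worse. Let μ0 and μ1 be the mediator means by arm in mothers to whom it applies. Regressing outcome on arm and mediator gives

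b_all = b + d × k, where k = p(1 - p) × (μ0 + μ1)/2 ÷ [(1 - p) + p(1 - p) × (μ0² + μ1²)/2].

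For a mediator used as a level, assume μ0 = 2 and μ1 = 2.5. The mean is 2.25 and the mean square is 5.125.

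- p = 0.10: k = 0.2025 / 1.3613 = 0.149
- p = 0.30: k = 0.4725 / 1.7763 = 0.266
- p = 0.50: k = 0.5625 / 1.7813 = 0.316

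| d | b_all at p = 0.10, 0.30, 0.50 | indirect effect, a_all × b_all |
|---|---|---|
| 0 | -0.300, -0.300, -0.300 | -0.135, -0.105, -0.075 |
| +1 | -0.151, -0.034, +0.016 | -0.068, -0.012, +0.004 |
| +2 | -0.002, +0.232, +0.332 | -0.001, +0.081, +0.083 |
| -1 | -0.449, -0.566, -0.616 | -0.202, -0.198, -0.154 |

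Simulations with 1,000,000 mothers agree with every row to within 0.002.

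**Step 3: mediator used as a slope.** This is closer to what 4.12 plans. If controls show no average change (μ0 = 0, μ1 = 0.5), k falls to 0.025, 0.072, 0.118. With d = +1, b_all is then -0.275, -0.228, -0.182: weakened, not reversed.

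If service use and substance use both fall on average by m slope SDs in the mothers to whom they apply, and both stay flat in the others, a true slope correlation r = -0.30 pools to (r + p·m²)/(1 + p·m²):

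- m = 0.5: (-0.30 + 0.075)/1.075 = -0.21 at p = 0.30, and (-0.30 + 0.125)/1.125 = -0.16 at p = 0.50;
- m = 1: (-0.30 + 0.30)/1.30 = 0.00 at p = 0.30, and (-0.30 + 0.50)/1.50 = +0.13 at p = 0.50.

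**Step 4: adjusting for track.** Adding track to both regressions returns b to -0.30 in every scenario of step 2, apart from simulation noise. The arm path stays at (1 - p) × a. Adjustment removes the confounding but not the dilution.

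**The case against.** The strongest reply is that the smaller arm path is not an error. If some mothers truly cannot move on this mediator, (1 - p)ab is the correct average indirect effect over everyone randomised, and wanting the effect in mothers to whom the mediator applies is a choice of estimand. That stands for step 1. It does not answer step 2, where b itself is biased for either estimand once the tracks differ on both variables.

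Several further limits also stand:

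- Zeros are not certain. Self-help groups count towards the indicator, and section 4.4 leaves mothers in both arms free to use community services.
- The general health-care items may pick up mental-health visits. The items are not shown, and the plan does not say how the self-care indicators are combined.
- Restriction buys little power. Under assumptions like these, at a 30% share, one simulation gave 67% for all mothers against 70% restricted, and another gave 70% for both.

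A reader might also infer more than the documents support:

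- **That stigma has the same flaw.** Section 4.4 says only "Stigma will be measured using a version of a Stigma scale". The file name "Modified Stigma Scale with Alcohol MSS.040913.docx" in 4.4.A suggests substance-specific items but does not show them.
- **That a zero will be scored as poor self-care.** No scoring direction is stated, and in a growth model a constant zero reads as no change.
- **That the mediated effect must shrink.** The d = -1 row shows inflation.

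**Conclusion.** The mismatch between eligibility and this one indicator is real, and nothing in 4.12 handles it. If mothers in mental-health care alone score zero in both arms, the arm-to-mediator path is diluted by their share, 10% to 50% over the range assumed. If the tracks also differ on the outcome, the mediator-to-outcome path is confounded. In the level scenarios, an indirect effect of -0.150 in the mothers concerned became anything from -0.202 to +0.083. In the slope scenarios the distortion ran from slight to a change of sign.

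The direction is therefore not fixed. The size depends on a share, a track difference and a scoring form that the documents do not give. Assignment does not depend on track, so the total treatment effects under Aims 1 and 2 are not biased; the problem is confined to interpreting Aim 3. It is worth correcting because the change is cheap, but it does not threaten the trial's main comparisons.

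**What to change.** In 4.12, state that mediation through use of substance abuse services is tested in mothers whose track before randomisation is substance abuse or co-occurring, with mothers in case management classified by the type of problem it addresses. Report an all-mother model adjusted for track as a sensitivity analysis.

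In 4.4, code not-applicable separately from zero. Do the same for mothers treated elsewhere who have no Banyan attendance record. State what the stigma items refer to, and apply the same restriction to stigma only if they prove to be substance-specific.

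The cost is plan wording and one baseline track variable, which staff must already establish to check criterion 1 in 5.7. The downside is a smaller mediation set: of 172 mothers, about 155, 120 or 86 would remain at shares of 10%, 30% or 50% (172 × 0.90, 0.70, 0.50). The result would apply only to substance abuse and co-occurring mothers.

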Mother's in recovery qualitative study. Thirteen mothers currently or recently discharged from substance abuse treatment at Banyan were interviewed regarding family influence on treatment, recovery and relapse, and attitudes/preferences regarding family aftercare. Preliminary review (formal content analysis is ongoing) suggests the following themes: 1) Children and family are the major motivation to remain substance-free; 2) Partner relationships, stress, family problems, shame/guilt, depression and environmental cues are the most challenging for abstinence; 3) Mothers want to involve supportive family members (especially children) in a home-based family aftercare intervention to address family healing, improve communication and support, establish family boundaries, re-establish maternal roles and repair parent-child relationships.

- 4.3. **If you have cited references above, please attach a bibliography, including title, full author list, journal, date and pages. This bibliography should include only those articles referenced above.**

Name	Description	Version
SET R Refs for IRB.docx		0.01

4a. Description of Study (cont'd)

Rationale and Methodology

- 4.4. *** In non-technical, lay language, describe the study design and all study procedures, in order of sequence and timing. Include length of subject participation, what tasks are involved in the study, what tests or procedures subjects will be asked to complete or undergo, specific measures to be used, etc. If applicable, include frequency of visits, duration of visits, and study procedure calendar.**

Study design: The study uses a mixed design in which mothers who are enrolled in outpatient substance abuse/mental health treatment (or treatment for substance abuse as a co-occurring condition) will be randomized to outpatient substance abuse/mental health (or co-occurring) treatment enhanced by Healthy Home (TAU + Healthy Home) or outpatient substance abuse/mental health (or co-occurring) treatment as usual (TAU). Mothers and their minor children enrolled in the study (ages 2-17) will be assessed 4 times at 4 month intervals: Baseline, 4 months, 8 months, and 12 months (with a window for final assessment up to 18 months). Randomization will take place after the baseline assessment.

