- The Healthy Home intervention integrates a family therapy approach, Structural Ecosystems Therapy (SET), with health services for mothers in substance abuse treatment and their children. Healthy Home is delivered by nurses through family visits. The nurse sees the family all at once, so that nursing care strengthens family unity. Visits take place approximately once every two weeks for a period of four months in the mother's home or other sites that are private and convenient to the family. Visits are ordinarily planned to include the mother, her children and some person(s) from the family and/or ecosystem (e.g., neighbor, friend).

During family visits the nurse attends to the health of the mother, children and other family members who are present. The nurse assesses family members' health needs, provides recommendations and education, and assists with referrals and access to services. The referrals for services may be to the nurse's own facility or to other service agencies. In between visits the nurse interacts with other service providers – e.g., the substance abuse counselor and mother and children's health care providers – to help optimize the family's use of these services and to help coordinate care. The nurse incorporates SET techniques into the delivery of these nursing functions as a means of strengthening family functioning. The family functions we are particularly interested are those that support the mother's substance abuse recovery, the mother's health and the care of the children.

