The three basic techniques in SET are joining, structural diagnosis, and restructuring. Joining refers to the process of establishing therapeutic alliances. Diagnosing refers to the identification of interactional patterns that contribute to the problems experienced by the mother, and thus need to be changed, as well as those that are sources of support and thus should be reinforced. Restructuring involves orchestrating opportunities for individuals to interact in ways that reinforce strengths and change maladaptive interactional patterns. Each Healthy Home case is tailored to the particular needs of the mother and her family. Healthy Home consists of three phases of treatment: initiation, treatment, and termination. Specific focus areas include: Substance abuse contexts, support and family status, couple relationships, parenting, and health/self-care. Healthy Home training will be conducted by [name] and another trainer. Healthy Home supervision will be ongoing and conducted by [name] and Banyan clinical supervisors.

-TAU consists of substance abuse outpatient treatment services normally offered by Banyan and other agencies where the women are receiving substance abuse or mental health services.

In addition to collecting measures from mothers and children, staff of the Banyan Health System will complete measures for assessment of study implementation factors. We do not believe that these measures constitute human subjects research and therefore do not consider

staff to be study participants. Measures are as follows:

- Healthy Home Treatment Fidelity. Healthy Home nurses will typically complete a fidelity checklist after each family visit.
- Implementation Costs will be obtained from invoices completed by agency administrators that cover the full range of costs involved in implementing Healthy Home, salaries (training, supervision, and delivery), materials, etc. Nurses will log all contacts with participants (phone calls, visits, time/location, purpose, etc.). Nurses will log the amount of time spent each week on cases that does not involve contact with participants, e.g., documentation, preparation, discussing cases with colleagues, training, etc.
- Satisfaction with Implementation will be assessed using a measure adapted from a previous substance use intervention study (Santisteban, 2008). Nurses, supervisors and agency administrators will rate their satisfaction with training, supervision, intervention, and impact on delivery of usual services.

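### Nurses deliver Healthy Home in one arm only and the growth models have no nurse term, so the standard error of the treatment effect is understated if outcomes differ between nurses

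*Combined protocol and SAP*

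**What the plan says.** Section 4.1 plans for "approximately 172 Black, Hispanic and White non-Hispanic mothers" and says that "agency nurses will deliver Healthy Home". Section 4.4 likewise states that "Healthy Home is delivered by nurses through family visits" and gives the contact pattern: "Visits take place approximately once every two weeks for a period of four months", which is roughly eight visits per family. On the other side, "TAU consists of substance abuse outpatient treatment services normally offered by Banyan and other agencies", and Section 4.5 confirms that Healthy Home comes on top of that same usual care. Mothers are randomized individually: "Randomization will take place after the baseline assessment".

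For the treatment comparison, Section 4.12 says that "LGM will examine the effect of treatment condition on trajectories of change separately for each of the outcomes", by intent to treat. The paragraphs there on growth models, hypothesis tests, moderators and missing data mention no nurse level, random effect, clustering or robust standard error. Nurse information is collected for other purposes: fidelity checklists, cost logs ("Nurses will log all contacts with participants"), satisfaction ratings and secondary analysis of clinical forms.

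The number of nurses, their caseloads, the rule for assigning families to nurses and the allocation ratio are not stated.

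**The concern.** When several families in one arm have the same nurse and the other arm has no nurse, the design is partially nested. Outcomes of families who share a nurse can be correlated, and a single-level growth model with condition as predictor does not allow for this. If the correlation is there, the interval for the treatment effect is too narrow and the test rejects too often.

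The protocol gives some reason to think nurses could matter. Section 4.4 describes a nurse who forms an alliance with the family, reshapes its interactions and tailors each case. Aim 4 in Section 4.1 relates fidelity to outcomes. A plan that looks for an effect of delivery quality should at least check whether outcomes vary between the people who deliver.

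**Working it through.** **Plan's own figure.** There is nothing to reproduce. Section 4.1 gives about 172 mothers, but the documents give no power calculation, target effect, standard deviation, dropout rate or ICC.

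**Inputs**
- Total of 172 mothers (Section 4.1).
- Assumed: 1:1 allocation, so 172 / 2 = 86 per arm.
- Assumed: k = 4 or 8 nurses with equal caseloads, m = 86 / k.
- Assumed: nurse ICC of 0, 0.01, 0.02 or 0.05.
- Assumed: two-sided 5% test, equal total variance in both arms, one mean comparison at one time point.

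**Formulas**
- Design effect in the Healthy Home arm: DE = 1 + (m − 1) × ICC. In the TAU arm it is 1.
- True variance of the difference: (σ²/86) × (DE + 1). The independence model uses (σ²/86) × 2.
- Ratio of true to reported standard error: r = √((DE + 1) / 2).
- Actual type I error: 2 × (1 − Φ(1.96 / r)).

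**One case in full.** With 4 nurses, m = 86 / 4 = 21.5. At ICC 0.05, DE = 1 + 20.5 × 0.05 = 2.025, so r = √(3.025 / 2) = 1.23. Then 1.96 / 1.23 = 1.59, and the type I error is 11.1%.

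| Nurses | Families per nurse | ICC | DE | SE ratio | Type I error |
|---|---|---|---|---|---|
| any | – | 0 | 1.00 | 1.00 | 5.0% |
| 4 | 21.5 | 0.01 | 1.21 | 1.05 | 6.2% |
| 4 | 21.5 | 0.02 | 1.41 | 1.10 | 7.4% |
| 4 | 21.5 | 0.05 | 2.03 | 1.23 | 11.1% |
| 8 | 10.75 | 0.01 | 1.10 | 1.02 | 5.6% |
| 8 | 10.75 | 0.02 | 1.20 | 1.05 | 6.1% |
| 8 | 10.75 | 0.05 | 1.49 | 1.12 | 7.9% |

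**Check by simulation.** With 20,000 simulated trials per setting, analysed by t test, the 4-nurse rejection rates were 5.9%, 7.0% and 11.2%, close to the formula.

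**What the figures do not cover.** They are not for growth slopes. Randomization follows baseline, so a nurse can affect only later change, and the relevant quantity is the nurse ICC of the growth parameters, on which the documents are silent. Mothers who never take up the visits stay in the intent-to-treat set and dilute any nurse clustering. An effect of about eight visits in four months may also fade by month 12. Siblings within a family are a separate level for the child outcomes and are not included.

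**The case against.** The strongest reply is that the problem may be small or absent. Healthy Home is manualized, with training, ongoing supervision and fidelity checklists, all of which tend to limit differences between nurses. At ICC 0.01 the type I error is 6.2% with 4 nurses and 5.6% with 8. If Healthy Home has no effect with any nurse, nurses add no correlation and there is no inflation by this route; inflation under the null needs nurse effects that differ but average to zero. One may also choose to make inferences about these nurses only, treating them as fixed. All of this stands, and it is why the point is conditional.

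Several stronger readings are tempting but not supported:
- A reader might infer that the intervals are certainly too narrow. That needs a nurse ICC above zero, which the documents neither show nor rule out.
- A reader might infer that the plan asserts independence. It is silent; independence is the default of the model described, in a short summary carried over from the grant application.
- A reader might take the remark in Section 4.12 about other agencies to mean that the effect is to be generalised to other nurses. That sentence concerns feasibility, judged from cost, satisfaction and fidelity.
- A reader might assume that the contact logs and progress notes already carry a nurse identifier. Since nurses write them this is likely, but no such field is described.

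What the objection does not remove is that the plan neither models nurse variation nor provides a way to see whether it matters.

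**Conclusion.** The point holds in conditional form. The one-arm nurse delivery and the lack of a nurse term are both in the documents; that families share nurses is a near-certain inference from a team of nurses serving about half of 172 families. If outcomes differ between nurses, following Section 4.12 as written understates the standard error. Over the ranges shown (4 or 8 nurses, ICC 0.01 to 0.05), the true standard error is 2% to 23% larger than reported, and the type I error is 5.6% to 11.1%. These figures rest on assumed 1:1 allocation, equal caseloads, assumed nurse numbers and ICCs, and a single-time-point comparison. The size for the planned trajectory tests is unknown and may be smaller. This justifies a sensitivity analysis; it does not call for a change to the design or to the main analysis.

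**What to change.** - State the number of nurses, their expected caseloads and how families are assigned to them.
- Record the treating nurse for each Healthy Home family in the analysis file. This is easier during the trial than afterwards.
- Beside the main intent-to-treat result for the main mother and child outcomes, report a partially nested sensitivity model: a nurse random effect in the Healthy Home arm only, with small-sample degrees of freedom, and the estimated nurse ICC. Nurse should not be an adjusting covariate across arms, since it exists in one arm only, and a plain cluster-robust standard error is unreliable with few nurses.
- If the nurses are too few to estimate the variance, show the effect with standard errors inflated over a stated ICC range that includes low values, for example 0.01 to 0.05, and say that the range is assumed.

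This is a cheap improvement: some wording in Section 4.12, one variable, and an extra model for each main outcome, with more work where the outcome is a count or binary. The downsides are wider intervals and an imprecise nurse variance (4 nurses leave 4 − 1 = 3 degrees of freedom). Because the assignment rule is not stated and contacts follow the family's language, that variance may partly reflect case mix. The fallback shows sensitivity only; it adds no information from the trial.
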